9. STATISTICAL CONSIDERATIONS AND METHODS

9.1. Sample Size Determination

A post hoc analysis was conducted using a subgroup of AUX-CC-871 subjects who were rated with moderate/severe AC based on baseline MRI images. This subgroup displayed a notable treatment effect (EN3835 vs placebo) on the pain and composite components of the adapted ASES questionnaire. This subgroup also displayed a treatment effect trend for the functional component of the adapted ASES. Given this result, the sample size calculation is based on the mean and SD found in this subgroup for the adapted ASES composite score on Day 95. Given a mean change from baseline value of 38.6 for the EN3835 group and 27.6 for the placebo group with an SD of 21.6, a sample size of approximately 142 subjects would be required given a 1:1 randomization and a type I error of 0.05 with a power of 85%. With an expected drop-out rate of approximately 20%, 180 subjects (90 EN3835 and 90 placebo) should be dosed to ensure 142 subjects complete the study.

9.2. **Populations for Analysis**

For the purposes of analysis, the following populations are defined:

- The Safety Population is defined as all randomized subjects who received at least 1 injection of study treatment (EN3835 or placebo). All safety analyses will be based on this population.
- The Intent-to-Treat (ITT) Population is defined as all randomized subjects who received at least 1 injection of study treatment (EN3835 or placebo).
- The Modified Intent-to-Treat (mITT) Population is defined as all ITT subjects who have a valid baseline adapted ASES composite score in the affected shoulder and at least 1 valid adapted ASES composite score after the injection of the study treatment. All efficacy analyses will be based on this population.
- The Per-Protocol (PP) Population is defined as those subjects in the mITT Population who do not have any major protocol deviations. Determination of PP subjects will be completed before the study database is closed and locked. If more than 10% of the mITT Population is excluded from the PP Population, then all efficacy summaries will be repeated using the PP Population for the sensitivity analysis.

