9.3.1. Efficacy Analysis

The primary endpoint is the change from baseline to the Day 95 Visit in the adapted ASES composite score.

A mixed-model ANOVA with factors for treatment group and visit will be performed to compare active to placebo for the change from baseline to the Day 95 Visit in adapted ASES composite score.

A mixed-model ANOVA with factors for treatment group and visit will be performed to compare active to placebo for the absolute and percent change from baseline to the Day 22, 43, 64, and Day 95 Visits in PROM, AROM, adapted ASES function subscale, and adapted ASES pain subscale.

For the Investigator Satisfaction with Treatment and Subject Satisfaction with Treatment at the Days 64 and Day 95 Visits, a Wilcoxon rank sum nonparametric test will be performed to compare active to placebo. A Wilcoxon rank sum nonparametric test will also be used to compare active to placebo for the change from baseline in Patient-reported Global Severity of Adhesive Capsulitis at the Day 22, 43, 64 and 95 Visits.

For Patient-reported Change in Severity of Adhesive Capsulitis at the Day 22, 43, 64, and 95 Visits, a chi-square test will be performed to compare active to placebo.

Endpoints of the affected shoulder in the EN3835 group will be compared to the endpoints of the affected shoulder in the placebo group.

The tertiary/exploratory analysis plan will be provided in the SAP.

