4.7.1.3. Composite Score

The adapted ASES composite score is the sum of the pain subscale score (50% of the composite score) and the function subscale score (50% of the composite score). The calculation is:

Composite score = Pain subscale score + Function subscale score

25-April-2022

The range for the composite score is 0-100, where 0 is the worst pain and least functional and 100 is least pain and most functional. If either of the pain subscale or function subscale score is missing, then the ASES composite score will be considered as missing.

Change from baseline in the adapted ASES composite score for the affected shoulder at the Day 22, 43, 64, and 95 Visits will be analyzed. Positive change from baseline score means an improvement in pain and/or shoulder function from baseline.

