6. STATISTICAL METHODS

6.1. General Methodology

All statistical tests, summary tables and data listings will be prepared using SAS version 9.3 or higher.

All statistical tests of efficacy parameters will be 2-sided with a significance level of α =0.05, unless specified otherwise. Statistical tests will be supported by presenting estimates and 95% confidence intervals (CI) for each treatment group.

Continuous data will be summarized using descriptive statistics (number of subjects [n], mean, SD, median, minimum, and maximum). Discrete data will be summarized using frequency counts and percentages. The denominator will be based on the number of subjects in the appropriate population.

For the purpose of display, the summary results will be rounded as follows:

- Minimum and maximum: Same number of decimal places as the raw data.
- Mean and Median: One more decimal place than the raw data.

- SD: Two more decimal places than the raw data.
- Percentages will be displayed with 1 decimal place precision. A zero count will be left blank.
- The standard form of a percentage change variable is 0 decimal places.

For categorical variables with missing values, a category documenting the frequency of missing values will be displayed in the summary tables.

Summary tables, subject listings, graphs and any supportive SAS output will include footnotes that will indicate:

- Date of data extraction.
- Date and time of output generation.
- SAS program name, including the path that generated the output.

When calculating percentages, the denominator will be based on the number of subjects with non-missing values. If the denominator is expected to change over time, then the denominator used to calculate the percentage will be based on the number of subjects with non-missing values at each visit. Any subject removed from an analysis will be noted at the bottom of the table along with the reason the subject was removed.

Empty summary tables will be presented with a note stating that "No Subjects Met Criteria."

Subject listings of all data from the eCRFs as well as any derived variables will be presented.

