7.9.1. Primary Analysis

7.9.1.1. Change from Baseline in Adapted ASES Composite Score

The primary endpoint is the change from baseline to the Day 95 Visit in the adapted ASES composite score.

MMRM will be performed to estimate change from baseline treatment effect at Day 64 and Day 95 Visits comparing active to placebo for the adapted ASES composite score in the affected shoulder. MMRM will be performed to estimate the least square (LS) means of change from baseline for EN3835 and placebo treatment. *P* values and 95% CIs for the treatment difference (EN3835 – Placebo) will be calculated by MMRM for the visits with treatment, visit, and an interaction of treatment and visit as fixed effected and repeated with visit/subject. Autoregressive covariance structure will be used in the model.

Observed values and change from baseline in the adapted ASES composite score in the affected shoulder for each treatment group will be summarized at Day 22, 43, 64 and 95 Visits using descriptive statistics.

A listing of adapted ASES scores will be provided.

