 - All arms with identical adjustment: $\delta_P = \delta_A$ and $\delta_A = 0$ to Δ_1
- The imputation will be performed using SAS PROC MI with the MONOTONE statement and the REGRESSION option with the following specifications:

```
PROC MI DATA=IN_MCMC NIMPUTE=1 (see note) SEED=234 OUT=OUTPUT;
VAR ...; (treatment group, baseline covariates, and the preceding non-missing values in
the order of clinical visits: baseline, Visit X, ..., Visit Y)
CLASS...; (treatment group)
MONOTONE REG (/details);
MNAR ADJUST (Visit X / SHIFT=delta_a ADJUSTOBS=(TRT01PN ='1'));
MNAR ADJUST (Visit Y / SHIFT=delta_a ADJUSTOBS=(TRT01PN ='1'));
MNAR ADJUST (Visit Y / SHIFT=delta_a ADJUSTOBS=(TRT01PN ='1'));
MNAR ADJUST (Visit X / SHIFT=delta_a ADJUSTOBS=(TRT01PN ='1'));
MNAR ADJUST (Visit X / SHIFT=delta_p ADJUSTOBS=(TRT01PN ='0'));
MNAR ADJUST (Visit Y / SHIFT=delta_p ADJUSTOBS=(TRT01PN ='0'));
MNAR ADJUST (... / SHIFT=delta_p ADJUSTOBS=(TRT01PN ='0'));
```

Note: NIMPUTE=n if MCMC was NOT applied at the previous step.

Step 3: Analysis and Pooling

For each value of δ_P and δ_A , MMRM described in section 7.9.1 will be performed for each of the n adjusted fully imputed datasets. The analysis results obtained will be combined into a single estimation using PROC MIANALYZE to produce final inferences.

The following estimates will be presented in the sensitivity analysis table:

- 1. LSM estimate for the mean change from baseline at the visit where primary endpoint is measured for each treatment.
- 2. LSM estimate for treatment difference of the mean change from baseline at the visit where primary endpoint is measured and the corresponding 2-sided 95% CI and p-value for change from baseline in the primary endpoint will be provided.

Shift parameters will begin with active-only adjustment, followed by a control adjustment that is half of the active adjustment, followed by all arms with identical shift adjustments, as stated in Step 2.

25-April-2022

All steps above are repeated with different values of the shift parameter until the tipping point is reached or all possible values are explored. The tipping point can be identified when the result is no longer statistically significant (p-value >0.05). It is possible a tipping point is not reached if little to no data is missing.

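### The primary MMRM fixes an autoregressive covariance with no form, fallback or robust SE; read as homogeneous first-order, it misstates the Day 95 standard error if the variance of change scores differs between visits

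*SAP*

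**What the plan says.** SAP 7.9.1.1 fits the primary MMRM "with treatment, visit, and an interaction of treatment and visit as fixed effected and repeated with visit/subject". On the covariance it says only "Autoregressive covariance structure will be used in the model". It does not say whether this is first-order, whether variances may differ by visit, or whether correlation runs by visit number or calendar time. It names no alternative structure, convergence rule, robust variance or degrees-of-freedom method. SAP 7.9.2.1 to 7.9.2.4 (PROM, AROM, the two ASES subscales, PUM) use the same sentence.

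The visits in the primary model are not settled either. Section 7.9.1.1 says "MMRM will be performed to estimate change from baseline treatment effect at Day 64 and Day 95 Visits", and mentions Days 22 and 43 only for descriptive summaries. SAP 7.9.2.1 to 7.9.2.3 name all four visits for their MMRMs, and SAP 4.7.1.3 says change in the "adapted ASES composite score for the affected shoulder at the Day 22, 43, 64, and 95 Visits will be analyzed".

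Protocol 9.3.1 names no covariance: "A mixed-model ANOVA with factors for treatment group and visit will be performed to compare active to placebo". SAP Table 17 does not list the choice as a change from the protocol. The tipping-point analysis in SAP 7.9.4.1 reuses the model: "MMRM described in section 7.9.1 will be performed for each of the n adjusted fully imputed datasets".

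**The concern.** The means are saturated: each treatment-by-visit cell has its own mean. With complete data the Day 95 estimate is therefore the plain difference in means, whatever the covariance, and the covariance affects only its standard error. A homogeneous first-order structure has one variance for all visits, so the Day 95 standard error borrows variance from earlier visits. If those visits are less variable than Day 95, the standard error is too small and the test rejects too often. If they are more variable, the interval is too wide and power is lost.

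The primary p-value and 95% CI rest on this standard error. The tipping-point analysis cannot reveal the problem, because it uses the same model and is run only if the primary result is significant (SAP 6.3.1).

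**Working it through.** **Inputs from the documents.** Protocol 9.1: "Given a mean change from baseline value of 38.6 for the EN3835 group and 27.6 for the placebo group with an SD of 21.6", so the difference is 38.6 − 27.6 = 11.0; 1:1 allocation; 85% power; about 20% dropout; 142 evaluable and 180 dosed. SAP 6.1: "All statistical tests of efficacy parameters will be 2-sided with a significance level of" 0.05. Composite visits are Days 22, 43, 64 and 95, with gaps of 21, 21 and 31 days.

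**Assumptions.** SDs before Day 95 and the between-visit correlations are not given, so a range is used.

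**Step 1: the plan's own figure.** The normal approximation gives 2 × (1.960 + 1.036)² × 21.6² / 11² = 69.2, so 70 per arm. The t-test needs 71 per arm, 142 in total (power 0.854). Allowing for dropout, 142 / 0.80 = 177.5, so 178 against the stated 180. The figure reproduces.

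**Step 2: standard error ratio, complete data.** The true Day 95 standard error at 71 per arm is 21.6 × √(2/71) = 3.63. Under homogeneous AR(1) the fitted variance is the mean of the visit variances (exactly for two visits, very nearly for four). So:

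- ratio r = √(mean of visit variances) / 21.6
- actual two-sided error = 2 × [1 − Φ(1.96 r)]
- power = Φ(11/3.63 − 1.96 r)

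For example, Day 64 SD 20.5 with Day 95 SD 21.6 gives √((420.25 + 466.56)/2) = 21.06; r = 21.06/21.6 = 0.975; error 5.6%.

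| Assumed SDs | Visits modelled | r | Type I error | Power |
|---|---|---|---|---|
| 21.6 throughout | 2 or 4 | 1.000 | 5.0% | 0.86 |
| 20.5 / 21.6 | Days 64, 95 | 0.975 | 5.6% | 0.87 |
| 19 / 21.6 | Days 64, 95 | 0.942 | 6.5% | 0.88 |
| 23 / 21.6 | Days 64, 95 | 1.033 | 4.3% | 0.84 |
| 17 / 19 / 20.5 / 21.6 | all four | 0.907 | 7.5% | 0.90 |
| 13 / 16 / 19 / 21.6 | all four | 0.819 | 10.8% | 0.92 |
| 26 / 24.5 / 23 / 21.6 | all four | 1.103 | 3.1% | 0.81 |

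The higher power in the rising rows comes only from a standard error that is too small. Fitting AR(1) by likelihood instead of using the formula gives 7.6%, 10.8% and 3.0% for the last three rows. A milder four-visit rise, from 18 to 21.6, gives 7.1%.

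**Step 3: does spacing matter?** AR(1) was fitted with flat SD 21.6 and a true correlation that decays by calendar day over the 21, 21 and 31-day gaps. The ratio is 1.000 and the error 5.0%. A compound-symmetric truth gives the same. With two visits there is only one lag, so spacing cannot enter.

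**Step 4: dropout.** Simulated four-visit trials had 90 per arm, 20% to 22% monotone missing-at-random dropout and 1,500 runs per scenario. AR(1) type I error was 4.6% to 4.9% with flat SDs, 6.0% to 6.5% with SDs rising from 18 to 21.6, and 8.5% to 9.7% rising from 15 to 21.6. Unstructured covariance gave 4.3% to 5.4%, with power 0.86 to 0.89. Falling SDs were not simulated here; those rows rest on the complete-data calculation.

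**The case against.** Four points can be made for the plan.

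1. *The SAP does not say one common variance.* A heterogeneous or spatial autoregressive form is not excluded. This stands: homogeneous AR(1) is the ordinary reading, not SAP text. But it leaves one sentence open to readings that can give different primary p-values, which is a defect in itself.
2. *The primary model probably has two visits.* The contrast between 7.9.1.1 and 7.9.2.1 to 7.9.2.3 favours this, and the distortion is then modest. This stands, although the text does not settle it. Change in the composite at all four visits is also a listed secondary endpoint, and it has no other inferential analysis in the SAP.
3. *Nothing shows that variance rises.* This stands. Entry requires a low function score and subjects may recover at different rates, which could widen the spread; the 0 to 100 bounds of the composite could narrow it. The documents give no SD before Day 95.
4. *Autoregressive correlation is harmless if variance is flat.* This also stands, as Steps 3 and 4 show. But the plan gives no reason to expect flat variance.

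A reader might also infer from the 21, 21 and 31-day gaps that unequal spacing invalidates the Day 95 inference. The calculation does not support that.

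**Conclusion.** The point holds as one of under-specification with a conditional effect. The SAP commits the primary test to an autoregressive structure without stating its form, the visits it covers or any safeguard. Under homogeneous AR(1), the Day 95 standard error is misstated whenever the variance of change scores differs between visits.

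With Day 95 SD 21.6 and assumed earlier SDs, type I error is about 5.6% to 6.5% (rising) or 4.3% (falling) for a two-visit model. For four visits it is about 7% to 11% (rising) or about 3% (falling, with power near 0.81 against 0.86). It is 5.0% if SDs are flat.

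It would be tempting to conclude that the trial's type I error is inflated to 7% or more. The documents do not support that: it needs the four-visit reading, the homogeneous reading and rising SDs together, and none of these is stated. The sign and size of the error are unknown. This should be fixed because the remedy is cheap; the primary analysis has not been shown to be invalid.

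**What to change.** In SAP 7.9.1.1, replace the autoregressive sentence with wording such as: *An unstructured covariance matrix with Kenward-Roger degrees of freedom will be used. If the model does not converge, heterogeneous Toeplitz and then heterogeneous autoregressive structures will be tried in that order, with a sandwich standard error for any structured form.* The fallback order is one reasonable convention; what matters is that it is fixed in advance. The simulations support the unstructured covariance and are not a separate test of the Kenward-Roger adjustment.

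In the same section, state which post-baseline visits enter the primary model. Make the same covariance change in 7.9.2.1 to 7.9.2.4; the tipping-point analysis then inherits it. List the covariance choice in Table 17.

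The cost is SAP wording and a few more parameters: 10 covariance parameters for four visits or 3 for two, against 2 for homogeneous AR(1). That is negligible with about 142 to 180 subjects, and the sample size does not change. The change belongs before unblinding, so that the structure is not chosen with the results in view.

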7.9.2. Secondary Analysis

7.9.2.1. Absolute and Percent Change from Baseline in PROM

MMRM will be performed to estimate change from baseline treatment effect at Day 22, 43, 64 and Day 95 Visits comparing active to placebo for PROM for forward flexion, internal rotation, external rotation, abduction, and shoulder extension in the affected shoulder. MMRM will be performed to estimate the LS means of absolute change from baseline for EN3835 and placebo treatment. *P* values and 95% CIs for the treatment difference (EN3835 – Placebo) will be

25-April-2022

calculated by MMRM for the visits with treatment, visit, and an interaction of treatment and visit as fixed effected and repeated with visit/subject. Autoregressive covariance structure will be used in the model.

MMRM will be performed to estimate absolute and percent change from baseline treatment effect compared to baseline of the contralateral shoulder at Day 22, 43, 64 and Day 95 Visits comparing active to placebo for PROM for forward flexion, internal rotation, external rotation, abduction, and shoulder extension in the affected shoulder. MMRM will be performed to estimate the LS means of absolute and percent change from baseline for EN3835 and placebo treatment. *P* values and 95% CIs for the treatment difference (EN3835 – Placebo) will be calculated by MMRM for the visits with treatment, visit, and an interaction of treatment and visit as fixed effected and repeated with visit/subject. Autoregressive covariance structure will be used in the model.

Observed values and change from baseline in PROM for forward flexion, internal rotation, external rotation, abduction, and shoulder extension in the affected shoulder for each treatment group at Day 22, 43, 64, and 95 Visits compared to the affected shoulder at baseline will be summarized using descriptive statistics.

Observed values, absolute and percent change from baseline in PROM for forward flexion, internal rotation, external rotation, abduction, and shoulder extension in affected shoulder for each treatment group at Day 22, 43, 64, and 95 Visits compared to the contralateral shoulder at baseline will be summarized using descriptive statistics.

A listing of PROM will be provided.

7.9.2.2. Absolute and Percent Change from Baseline in AROM

MMRM will be performed to estimate change from baseline treatment effect at Day 22, 43, 64 and Day 95 Visits comparing active to placebo for AROM for forward flexion, internal rotation, external rotation, abduction, and shoulder extension in the affected shoulder. MMRM will be performed to estimate the LS means of absolute change from baseline for EN3835 and placebo treatment. *P* values and 95% CIs for the treatment difference (EN3835 – Placebo) will be calculated by MMRM for the visits with treatment, visit, and an interaction of treatment and visit as fixed effected and repeated with visit/subject. Autoregressive covariance structure will be used in the model.

MMRM will be performed to estimate absolute and percent change from baseline treatment effect compared to baseline of the contralateral shoulder at Day 22, 43, 64 and Day 95 Visits comparing active to placebo for AROM for forward flexion, internal rotation, external rotation, abduction, and shoulder extension in the affected shoulder. MMRM will be performed to estimate the LS means of absolute and percent change from baseline for EN3835 and placebo treatment. *P* values and 95% CIs for the treatment difference (EN3835 – Placebo) will be calculated by MMRM for the visits with treatment, visit, and an interaction of treatment and visit as fixed effected and repeated with visit/subject. Autoregressive covariance structure will be used in the model.

Observed values and change from baseline in AROM for forward flexion, internal rotation, external rotation, abduction, and shoulder extension in the affected shoulder for each treatment

group at Day 22, 43, 64, and 95 Visits compared to the affected shoulder at baseline will be summarized using descriptive statistics.

Observed values, absolute and percent change from baseline in AROM for forward flexion, internal rotation, external rotation, abduction, and shoulder extension in the affected shoulder for each treatment group at Day 22, 43, 64, and 95 Visits compared to the contralateral shoulder at baseline will be summarized using descriptive statistics.

A Wilcoxon rank sum nonparametric test will be used to compare EN3835 to placebo for the HBB change from baseline values for active internal rotation in affected shoulder at the Day 22, 43, 64 and 95 Visits.

The null and alternative hypotheses for this test will be as below:

H₀: There is no difference in the change in baseline HBB values for active internal rotation in the 2 treatment groups.

Vs

H₁: The change in baseline HBB values for active internal rotation differs in the 2 treatment groups.

The Wilcoxon scores (Rank Sums) for treatment groups and test statistics along with p value for the test of significance will be presented.

Responses for HBB assessment for internal rotation will be summarized for each treatment group using frequency counts and percentages.

A listing of AROM will be provided.

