8.1.2. Range of Motion

PROM (for forward flexion, internal rotation, external rotation, abduction, and shoulder extension) and AROM (for forward flexion, internal rotation, external rotation, abduction, and shoulder extension) will be measured using a goniometer, and a spinal level (for internal rotation) at times specified in the Schedule of Activities for the affected and contralateral shoulder. These measurements will be completed with the subject in the supine position.

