3.15.2. Range of Motion (ROM)

PROM and AROM will be measured for the affected and contralateral shoulder at times specified in the SoA (Table 2) using a goniometer. The below range of motion measurements will be recorded:

- Forward flexion.
- Internal rotation.
- External rotation.
- Abduction.
- Shoulder extension.

The unit to measure PROM and AROM is degrees (°).

In addition, Hand Behind the Back (HBB) assessment will be performed for active internal rotation. The response for HBB assessment will be free text with no unit.

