4.7.2. Passive Range of Motion (PROM) and Active Range of Motion (AROM)

The PROM and AROM in affected shoulder at Day 22, 43, 64 and 95 will be analyzed for the following motions:

- Forward flexion.
- Internal Rotation.
- External rotation.
- Abduction.
- Shoulder extension.

The PROM and AROM will be analyzed at Day 22, 43, 64 and 95 using the following endpoints:

- Absolute change from baseline in affected shoulder
- Absolute and percent change from baseline in affected shoulder compared to the contralateral shoulder. The calculation is as below:

Let

ASi: Measurement from affected shoulder at visit i

CS1: Measurement from contralateral unaffected shoulder at baseline

then

Di = ASi - CS1

D1 (Baseline value) = AS1 - CS1

Absolute change = Di - D1

Percent change from baseline at Visit i = ((Di - D1) / D1) * 100

In addition, the HBB values will be ordinal ranked based on the level a subject can reach behind the back. The higher ranked assessment value signifies the ability to reach higher up behind the back. The lower the ranked value signifies the ability to reach behind the back low. A value of 0 will be assigned to subjects that cannot reach behind the back at all (the lowest rank possible).

The observed and change from baseline in HBB values will be analyzed at the Day 22, 43, 64 and 95 Visits.

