6.2. Derived Variables

Table 16 defines the derived variables for study parameters.

Variable	Definition	
Height (cm)	If height is recorded in inches, then height is equal to the recorded value multiplied by 2.54 and then rounded to 1 decimal place.	
Weight (kg)	If weight is recorded in pounds, then weight is equal to the recorded value multiplied by 0.454 and then rounded to 1 decimal place.	
Body Mass Index (BMI)	BMI will be computed using height and body weight measured at Screening as, BMI $(kg/m^2) =$ Weight $(kg) /$ Height $(m)^2$	
Relative Day 1	The day of first injection of study drug will be considered as relative Day 1.	
Study Day (for assessment on or after Day 1)	Study Day will be computed as, Date of Assessment – Date of Day 1 + 1	
Study Day (for assessment before Day 1)	Study Day will be computed as, Date of Assessment – Date of Day 1	
Baseline	Baseline is defined as the last non-missing measurement/assessment prior to the first dose of study drug.	
	The assessments made in unscheduled visits will be considered in calculation of baseline, if the unscheduled assessment is the closest value preceding the first dose of study drug.	
Baseline for Vital Signs on Injection Days	For vital signs on injection days, the baseline value will be the vital sign measure immediately prior to the first dose of study drug.	
Change from Baseline	Change from baseline will be derived as, post-baseline visit/time point value – the baseline value.	
Last Date in Study	Last date in study is defined as:	
	• The date of End of Study (EOS) Visit (Day 95) if the subject completes the study	
	• The date of early termination visit if the subject is terminated early from study at a non-scheduled visit	
	• The date of the latest scheduled visit if the subject is terminated early from study at a scheduled visit or lost to follow-up.	
Duration of AE	AE end date – AE start date + 1	
AE Onset Day (for AE onset date on or after date Day 1)	AE start date – Date of Day 1 + 1	
AE Onset Day (for AE onset date before date of Day 1)	AE start date – Date of Day 1	

Table 16:Derived Variables and Definition

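### The hand-behind-back (HBB) test subtracts ordinal ranks of free-text levels, so its result depends on an unlisted coding of the levels; baseline adjustment and a fixed level list would be a minor, near-free improvement

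*SAP*

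**What the plan says.** SAP 3.15.2 adds an HBB assessment for active internal rotation: "The response for HBB assessment will be free text with no unit". SAP 4.7.2 then states that "the HBB values will be ordinal ranked based on the level a subject can reach behind the back", with a higher rank for a higher reach and 0 as the floor for subjects who cannot reach behind the back. The same section adds: "The observed and change from baseline in HBB values will be analyzed at the Day 22, 43, 64 and 95 Visits". SAP 6.2 defines change as the post-baseline value minus the baseline value.

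SAP 7.9.2.2 applies a Wilcoxon rank sum test "to compare EN3835 to placebo for the HBB change from baseline values for active internal rotation in affected shoulder" at each of the four visits, with no baseline covariate, and presents rank sums, a test statistic and a p value. It also says: "Responses for HBB assessment for internal rotation will be summarized for each treatment group using frequency counts and percentages". No test is attached to those frequencies.

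Protocol 8.1.2 mentions a spinal level for internal rotation but does not name HBB. Neither document lists the levels, maps text entries to ranks, or says whether neighbouring levels may share a rank.

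**The concern.** The SAP declares the scale ordinal, so only the order of levels carries meaning. Subtracting ranks treats the steps as equal. The Wilcoxon test does not remove this difficulty. It is unaffected by order-preserving recoding of the variable it tests, but that variable is already a difference of ranks, and recoding the levels can change the order of the differences.

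Two things follow. The p value depends on the level list, which carries no information about treatment. And the baseline measurement, already collected, is used only by subtraction, which can be less efficient than using it as a covariate.

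**Working it through.** **The plan's own figure.** The documents give no power or sample size for HBB. The primary-endpoint calculation (SAP 3.5: difference 38.6 − 27.6 = 11.0, SD 21.6, two-sided 0.05, power 85%) supplies the number per arm used below. The normal formula n = 2(1.960 + 1.036)² × 21.6² / 11² gives 69.2, so 70 per arm. The t-test version gives 70.2, so 71 per arm and 142 in total, as stated.

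**Dependence on the list, without merging.** Take ordered levels a0 (cannot reach), a1, a2, and so on, ranked 0, 1, 2, … Subject A moves a0 to a2 (change 2). Subject B moves a5 to a8 (change 3). Now let the list include one extra landmark just below each of a1, a2 and a3. The ranks of a0 to a8 become 0, 2, 4, 6, 7, 8, 9, 10, 11. A's change is now 4 and B's is 11 − 8 = 3, so the order is reversed.

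**Dependence on merging.** Moves from level 2 to 6 and from level 10 to 15 are changes of 4 and 5 with single-level ranks. If levels are grouped as 0 / 1–2 / 3–4 / 5–7 / 8–11 / 12–17, they become 3 − 1 = 2 and 5 − 4 = 1. The order is again reversed.

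**Efficiency, one rank per level.** On an untransformed scale, with slope b of follow-up on baseline, residual variance σe² and baseline variance σB²:

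- variance for the change comparison = σe² + (1 − b)²σB²
- variance for the baseline-adjusted comparison = σe²

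The two are equal at b = 1, and change does worse as b falls. If baseline and follow-up have equal SDs, b equals the correlation ρ and the ratio of adjusted to change variance is (1 + ρ)/2: 0.65, 0.75 and 0.85 at ρ = 0.3, 0.5 and 0.7.

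Simulated power with 71 per arm and a true shift of 1.5 levels. All HBB inputs are assumptions.

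| Assumed baseline mean / SD | Slope | Wilcoxon on change | Rank ANCOVA | Gain (points) |
|---|---|---|---|---|
| 5 / 3.5, equal SDs | 0.3 | 57.0% | 73.0% | 16.0 |
| 5 / 3.5, equal SDs | 0.5 | 71.0% | 80.9% | 9.9 |
| 5 / 3.5, equal SDs | 0.7 | 88.7% | 91.1% | 2.4 |
| 3.5 / 2.2, error SD 3 | 0.6 | 79.1% | 82.8% | 3.7 |
| 3.5 / 2.2, error SD 3 | 0.8 | 81.4% | 81.4% | 0.0 |
| 3.5 / 2.2, error SD 3 | 1.0 | 82.1% | 80.9% | −1.2 |
| 6 / 3.5, error SD 3 | 0.8 | 79.3% | 79.2% | −0.1 |
| 6 / 3.5, error SD 3 | 1.0 | 81.9% | 81.0% | −0.9 |

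Trials per row: 4,000 (equal SDs), 3,000 (slope 0.6), 2,000 (the rest). At 2,000 trials the standard error of a power near 80% is √(0.8 × 0.2 / 2000) = 0.9 points, so differences of about 1 point are close to noise. A further run at slope 0.4 with baseline SD 3.5 gave a gain of about 15 points.

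**Other codings.** In the slope 0.6 model, counting the three lowest steps double cut the power of the change test from 79.1% to 72.0%, and the verdict at 0.05 differed in 9% of trials. Rank ANCOVA gave identical p values under both codings. Grouping by spinal region cut the change test to 40.4% and rank ANCOVA to 74.2%. Rank ANCOVA's verdict changed with grouping in about 13% to 20% of trials.

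**Type I error.** With no treatment effect, the change test rejected in 4.4% to 5.3% of trials in the equal-SD model, whatever the coding. Rank ANCOVA was also near 5%.

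**The case against.** The strongest reply is that SAP 4.7.2 reads naturally as one consecutive rank per level. Regional grouping would give different reaches the same rank, and double-counted steps are scores, not ranks. The large losses come from those codings. This stands, and the size of the point should not rest on them. What survives is that, even with consecutive ranks, the spacing is set by the length of the list, and the list is not given.

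Second, the list may be in the Study Operations Manual (Protocol 8.1) or SAP Module 2 (SAP 11), neither of which was supplied. If so, the choice of coding disappears. The subtraction of ordinal ranks does not.

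Third, omitting baseline as a covariate is not peculiar to HBB. The SAP's other change-score models list none, and global severity is also a Wilcoxon test on change (SAP 7.9.2.5). That is true. But the dependence on an unlisted set of levels is specific to HBB.

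Fourth, a different test alone would not cure the coding problem, because rank ANCOVA is unaffected only by recodings that keep levels distinct. This stands, and it is why the list must be fixed as well.

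**Conclusion.** The point holds as a minor one. The HBB result depends on the spacing or grouping of levels that the supplied documents do not list, and baseline is used only by subtraction. That dependence is arithmetic and needs no assumed effect. The power cost is an assumption-driven range: with one rank per level, from none (or a 1 to 2 point advantage for change) at a slope near 1 to about 15 points at a low slope, and larger if levels are merged.

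A reader might infer more, in four ways that the documents do not support:

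- **That the test gives false positives.** It does not: type I error is kept for any fixed coding.
- **That power is certainly lost, or falls to about 40%.** The first is not established and the second needs a grouping that fits SAP 4.7.2 poorly.
- **That internal rotation has no other test.** Active and passive internal rotation in degrees are each tested by MMRM at four visits (SAP 7.9.2.1, 7.9.2.2), and the ASES function items cover related activities.
- **That the coding will be chosen after seeing the results.** Nothing in the documents shows this; they are only silent on the list.

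HBB is not named in the endpoint tables. The primary endpoint and the sample size are unaffected.

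**What to change.** 1. In SAP 4.7.2, set out before unblinding an ordered list of HBB levels with one rank per distinct level and no merging, plus a map from free-text entries to ranks. If the list already exists in the Study Operations Manual or SAP Module 2, cite it.
2. In SAP 7.9.2.2, replace the Wilcoxon test of HBB change with a comparison of the HBB level at each visit, with baseline level as covariate, by rank analysis of covariance. A proportional-odds model reporting the common odds ratio and 95% CI is an alternative, at the price of a proportionality assumption.
3. Keep change in HBB as a descriptive or supportive summary.

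The cost is a paragraph of SAP text, the list itself and one different SAS procedure. No new data are needed. The downside is small: little or no power gain, or a loss of 1 to 2 points, if the slope of follow-up on baseline is near 1.
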